1 INTRODUCTION

This statistical analysis plan (SAP) defines the scope of the statistical analyses and provides a detailed description of the statistical methodology for subject data obtained in this substudy of PA0012. The SAP is based on the following study documents:

- Protocol amendment DV0004, 14 May 2020,
- Electronic Case Report Form PA0012_DV0004 (v6.0), 03 June 2020.

All references to the study protocol hereafter refer to this version of the protocol.

To avoid premature unblinding of the PA0010 and PA0011 Feeder Study treatment allocation, a Blinding Maintenance Plan has been created for the PA0012/DV0004 studies. Please refer to this document for specifics regarding the handling of pharmacokinetic and pharmacodynamic data. The blinding plan is only applicable until both feeder studies have unblinded.

2 PROTOCOL SUMMARY

2.1 Study objectives

2.1.1 Primary objective

The primary objective of the study is to evaluate for each self-injecting device the ability of subjects with psoriatic arthritis (PsA) to safely and effectively self-inject bimekizumab 4 weeks after training in the self-injection technique using the 1mL bimekizumab safety syringe (bimekizumab-SS-1mL) or the 1mL bimekizumab auto-injector (bimekizumab-AI-1mL).

2.1.2 Secondary objective

The secondary objective of the study is to evaluate the ability of subjects with PsA to safely and effectively self-inject bimekizumab immediately after training in the self-injection technique using the bimekizumab-SS-1mL or the bimekizumab-AI-1mL.

2.1.3 Other objectives

Other objectives of the study are to evaluate the following:

- Subject experience of self-injection as assessed by the pain visual analogue scale (VAS) for injection site pain and the Self-injection Assessment Questionnaire (SIAQ)
- Trough pharmacokinetic (PK) (trough bimekizumab) levels associated with self-injection using the test self-injecting device, injection by study personnel using the 1mL prefilled syringe (PFS), injection site (abdomen or thigh), and body mass index (BMI) category (by tertile)
- Immunogenicity of bimekizumab associated with self-injection using the self-injecting device presentations and injection by study personnel using the 1mL PFS
- The structural and mechanical integrity of the bimekizumab-SS-1mL and the bimekizumab-AI-1mL after completion of self-injection
- The functional integrity of the bimekizumab-SS-1mL and the bimekizumab-AI-1mL after completion of self-injection

- The overall safety and tolerability of self-injections using the self-injecting device presentations.

2.2 Study variables

2.2.1 Outcome variables

2.2.1.1 Primary outcome variable

The primary outcome variable is the ability to self-administer safe and effective injections using the bimekizumab-SS-1mL or the bimekizumab-AI-1mL at Week 4.

Safe and effective self-injection will be evaluated by the study personnel and is defined as:

- Complete dose delivery: Subject self-injects the complete dose of bimekizumab as confirmed by a visual inspection of the bimekizumab-SS-1mL or the bimekizumab-AI-1mL, which shows that the investigational medicinal product (IMP) is delivered completely (i.e., container is empty), and
- No adverse device events (ADEs) that would preclude continued use of the device for self-injection (i.e., no serious adverse device events [SADEs] and/or ADEs leading to withdrawal from the DV0004 substudy).

2.2.1.2 Secondary outcome variable

The secondary outcome variable is the ability to self-administer safe and effective injections using the bimekizumab-SS-1mL or the bimekizumab-AI-1mL at DV0004 Baseline (for first self-injection visit, immediately after training in the self-injection technique).

Safe and effective self-injection will be evaluated by study personnel and is defined using the same criteria as the primary outcome variable (see Section [2.2.1.1](#)).

2.2.1.3 Other variables

2.2.1.3.1 Outcome variables

The other outcome variables are:

- Responses to pre-injection SIAQ (versions 2.0 and 2.1) at DV0004 Baseline
Whenever SIAQ is assessed, version 2.0 of the SIAQ will be used to assess bimekizumab-SS-1mL and version 2.1 of the SIAQ will be used to assess bimekizumab-AI-1mL.
- Injection site pain (using a VAS; 100mm) by visit after self-injection using the assigned self-injecting device presentations at DV0004 Baseline and Week 4.
- Responses to post-injection SIAQ (versions 2.0 and 2.1) by visit following self-injection using the assigned self-injecting device presentations at DV0004 Baseline and Week 4.
- The structural and mechanical integrity of the bimekizumab-SS-1mL and the bimekizumab-AI-1mL after completion of the self-injection using the assigned self-injecting device presentations. This is based on a visual examination of the device that shows clear evidence of damage and/or compromised structural or mechanical integrity.

- The functional integrity of the bimekizumab-SS-1mL and the bimekizumab-AI-1mL after completion of self-injection using the assigned self-injecting device presentations. This is based on a visual examination of the device that shows clear evidence of damage and/or compromised functional integrity.

2.2.1.3.2 Pharmacokinetic variable

The PK variable is trough PK (bimekizumab) levels associated with self-injection using the test self-injecting device presentations, injection by study personnel using the 1mL PFS, injection site (abdomen or thigh), and BMI category (by tertile). Trough levels will be assessed at DV0004 Baseline, DV0004 Week 4, and PA0012 Week 8.

2.2.1.3.3 Immunological variable

The immunological variable is the anti-bimekizumab antibody, which will be collected as described in the PA0012 study protocol.

2.2.1.3.4 Safety variable

The other safety variable is the occurrence of ADEs. An ADE is an adverse event (AE) related to the use of an investigational device. An ADE must meet 1 or more of the following criteria:

- Adverse event resulting from insufficiencies or inadequacies in the instructions for use (IFU), the deployment, the implantation, the installation, the operation, or any malfunction of the investigational medical device.
- Adverse event that is a result of a use error or intentional misuse of the investigational device.

Additional safety and tolerability variables will be collected as described in the PA0012 study protocol.

2.3 Study design and conduct

2.3.1 Study description

DV0004 is a Phase 3, multicenter, open-label, randomized, noncomparator, North America and Europe substudy to PA0012. PA0012 will evaluate the long-term safety, tolerability, and efficacy of 160mg bimekizumab every 4 weeks (Q4W) in adult subjects with PsA; study personnel will administer bimekizumab to subjects in a 1mL PFS. The DV0004 substudy will evaluate 2 self-injection investigational devices: the 1mL bimekizumab-SS-1mL and the 1mL bimekizumab-AI-1mL.

In the DV0004 substudy, the safe and effective use of the bimekizumab-SS-1mL or the bimekizumab-AI-1mL for the sc self-injection of bimekizumab solution by adult subjects with PsA will be evaluated.

Subjects from selected sites in the PA0012 feeder studies, PA0010 and PA0011, will be eligible for the DV0004 substudy. The DV0004 substudy will maintain all study assessments of the main PA0012 study from DV0004 Baseline to Week 4 (inclusive). However, only subjects in the DV0004 substudy will self-administer bimekizumab using the bimekizumab-SS-1mL or the bimekizumab-AI-1mL at DV0004 Baseline and Week 4. At DV0004 Baseline, each subject will be provided with training in self-injection and will receive the IFU and any other applicable

training materials. Subjects in the DV0004 substudy will perform self-injections at the DV0004 Baseline (corresponding to the Entry Visit of PA0012) with a subsequent self-injection at the DV0004 Week 4 Visit (corresponding to Week 4 of PA0012).

2.3.2 Treatment Period

During the 4-week Treatment Period of DV0004, subjects will receive bimekizumab 160mg Q4W. This dose regimen will remain stable for the entire 4-week Treatment Period of DV0004 (consistent with PA0012).

Eligible subjects will be randomly assigned in a 1:1 ratio to perform self-injection using either the bimekizumab-SS-1mL or the bimekizumab-AI-1mL. Subjects will perform self-injection with the assigned device presentation at DV0004 Baseline (corresponding to the Entry Visit of PA0012) and at Week 4 (corresponding to Week 4 of PA0012). After Week 5 of the DV0004 substudy, subjects will continue in PA0012 (the next visit after DV0004 completion will be the Week 8 Visit in PA0012).

2.3.3 Safety Follow-Up

A device Safety Follow-up (SFU) telephone call will occur 1 week after the last self-administration (at Week 5). Subjects who are withdrawn from DV0004 but continue their PA0012 study participation will be required to perform an SFU telephone call 1 week after their final DV0004 dosing visit.

2.3.4 Withdrawal

Subjects who are withdrawn from bimekizumab treatment (PA0012 study) during the course of DV0004 will also be required to follow the PA0012 withdrawal procedures that means subjects will undergo the Early Termination (ET) Visit assessments and will enter the SFU Period.

2.3.5 Study duration per subject

The maximum DV0004 substudy duration will be 4 weeks for each subject. Subjects will then continue to receive treatment in PA0012 for the duration of the PA0012 study. The end of the DV0004 substudy is defined as the date on which the last subject completes his/her DV0004 Week 4 Visit or withdraws from the study.

2.3.6 Planned number of subjects

It is planned to enroll approximately 200 subjects; each device presentation arm will consist of approximately 100 subjects. It is anticipated that this study will involve up to 150 sites in North America and Europe.

2.4 Determination of Sample Size

This study will not be powered with respect to any endpoint, and sample size is based on practical considerations. In order to maintain blinding in the PA0012 feeder studies (PA0010 and PA0011), DV0004 will recruit all subjects who complete the PA0010 and PA0011 studies (including those treated with a comparator or placebo in the feeder study) up to a total of about 200 subjects. A total of 100 subjects (50 subjects per device presentation arm) are planned for PK trough level analyses, but these analyses will only be performed on subjects who were treated

with bimekizumab 160mg Q4W (i.e., not with placebo or comparator) to ensure that 100 subjects with stable (160mg Q4W bimekizumab) PK trough levels are available for PK trough analysis.

Subjects who enroll in the DV0004 substudy will be randomly assigned to the bimekizumab-SS-1mL or the bimekizumab-AI-1mL device presentation arms (each device presentation arm will consist of approximately 100 subjects). Within each device presentation arm, subjects will be divided into tertiles by BMI; there will be approximately 33 subjects per tertile, which is expected to yield approximately 16 to 17 subjects per tertile who are evaluable for steady state trough PK level analyses (approximately 100 subjects in total).

3 DATA ANALYSIS CONSIDERATIONS

3.1 General presentation of summaries and analyses

Statistical analysis and generation of tables, figures, subject data listings, and statistical output will be performed using SAS Version 9.3 or higher. All tables and listings will use Courier New font size 9.

Descriptive statistics will be displayed to provide an overview of the study results. For continuous variables, descriptive statistics will include number of subjects with available measurements (n), mean, standard deviation (SD), median, minimum, and maximum.

For categorical variables, the number and proportion of subjects, will be presented. In addition, for the primary, secondary and other variables the 90% confidence interval (CI) based on the Exact Binomial, will also be presented. Unless otherwise noted, the denominator for percentages should be based on the number of subjects included in the respective analysis set. Subjects with missing data can generally be accounted for using either of the following approaches:

- For summaries of demographics and Baseline characteristics: summarize percentages based on all subjects in the analysis set and include a “Missing” category (corresponding to subjects with missing data for the variable being summarized) as the last row in the list of categories being summarized.
- For summaries of outcome and safety variables, unless otherwise specified: percentages will be summarized based only on those subjects with observed data for the variable being summarized. As the denominator may be different from the number of subjects in the analysis set being considered, the denominator should be displayed in the table. The general format for displaying this will be “n/NSub (%)”, unless otherwise specified.

Percentages will be presented to 1 decimal place. If the percentage is 100 or 0, no decimal will be presented. Typically, the % sign should be presented in the column header, but not with each individual value.

For bimekizumab PK concentrations, summary statistics will include geometric mean, geometric coefficient of variation (CV), 95% confidence intervals for geometric mean, arithmetic mean, SD, median, minimum, and maximum. All summaries of PK variables will be based on the observed values. No imputation will be used.

Decimal places for descriptive statistics will always apply the following rules:

- “n” will be an integer

- Mean, SD, and median will use one additional decimal place compared to the original data
- CV [%] will be presented with one decimal place
- Minimum and maximum will have the same number of decimal places as the original value.

Derived variables in general will display the mean, SD, and median to 1 more decimal place than the variables used in the derivation. If the number of decimal places reported in the raw data is varied, then use either the maximum raw number of reported decimal places or 3, whichever is the lowest, as a guide for the descriptive statistics.

A complete set of data listings containing all documented data as well as calculated data will be generated.

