4 STUDY VARIABLES

4.1 Outcome variables

4.1.1 Primary outcome variable

The primary outcome variable is the ability to self-administer safe and effective injections using the bimekizumab-SS-1mL or the bimekizumab-AI-1mL at Week 4. Safe and effective self-injection will be evaluated by the study personnel and is defined as:

- Complete dose delivery. Subject self-injects the complete dose of bimekizumab as confirmed by a visual inspection of the bimekizumab-SS-1mL or the bimekizumab-AI-1mL which shows that the IMP is delivered completely (ie, container is empty), and
- No ADEs that would preclude continued use of the device presentations for self-injection (ie, no S.ADEs and/or ADEs leading to withdrawal from the DV0004 substudy).

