11.1 Primary outcome variable

The primary outcome variable is the percentage of all subjects able to self-administer safe and effective injections using the given device at DV0004 Week 4. Safe and effective self-injection will be evaluated by the study personnel as defined below:

- Complete dose delivery: Subject self-injects the complete dose of bimekizumab as confirmed by a visual inspection of the bimekizumab-SS-1mL or the bimekizumab-AI-1mL which shows that the IMP is delivered completely (i.e., the container is empty), and
- No ADEs that would preclude continued use of the device presentations for self-injection (i.e., no SADEs and/or ADEs leading to withdrawal from the DV0004 substudy).

All data to assess the primary outcome is collected on the subject self-injection of bimekizumab CRF page for DV0004 Week 4. For the number of subjects with safe and effective self-injections simply the cases which indicated “yes” for the question “Did the subject self-inject the complete dose of Bimekizumab” and “no” for the question “Were there any AEs related to use of the investigational device for self-injection” at DV0004 Week 4 are counted.

The number and percentage of subjects with safe and effective self-injections will be tabulated separately for each device presentation using the relevant FAS population (FAS-s or FAS-a). The 90% CIs based on the Exact Binomial method will be reported as well. The number and percentage of subjects with safe and effective self-injections is tabulated for each device presentation by COVID-19 enrollment period, as described in Section 4.9.1.

Assessments where the self-injection was not performed by the subject will not be included in any summary statistics.

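### Under the SAP's observed-data rule, a subject who withdraws for an adverse device effect after the Baseline injection leaves the Week 4 primary percentage, although the endpoint definition makes that event a failure

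*SAP*

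**What the plan says.** **Definition.** Protocol 4.1.1 requires complete dose delivery and "No ADEs that would preclude continued use of the device presentations for self-injection". SAP 11.1 spells the second part out as "no SADEs and/or ADEs leading to withdrawal from the DV0004 substudy". SAP 3.8, which lists changes from the protocol, does not alter this definition.

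**Data source and count.** SAP 11.1 states: "All data to assess the primary outcome is collected on the subject self-injection of bimekizumab CRF page for DV0004 Week 4". A success is a yes to the complete-dose item and a no to "Were there any AEs related to use of the investigational device for self-injection" on that page. The section adds: "Assessments where the self-injection was not performed by the subject will not be included in any summary statistics".

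**Denominator.** SAP 3.1 first sets a default: "Unless otherwise noted, the denominator for percentages should be based on the number of subjects included in the respective analysis set". For outcome and safety variables it then says that, unless otherwise specified, "percentages will be summarized based only on those subjects with observed data for the variable being summarized", and that the denominator is to be displayed. SAP 11.1 names no denominator, but describes the outcome as the "percentage of all subjects able to self-administer safe and effective injections using the given device at DV0004 Week 4" and tabulates it on the FAS.

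**FAS and missing data.** One assessed self-injection is enough to enter the FAS (SAP 3.4.3). Protocol 14.2 rules out imputation. SAP 4.2 has no missing-data procedure that would reach this outcome.

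**The concern.** DV0004 has two self-injections, at Baseline and at Week 4. An ADE from the first that makes the subject leave the substudy does so before the second. That subject is in the FAS and has had an event that the definition names as a failure. The counting rule, however, looks only at the Week 4 page, where this subject has no self-injection to assess.

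If the observed-data rule governs, the primary percentage leaves out a failure that the endpoint was written to include. The study is purely one of estimation, so the percentage and its 90% interval are the primary result. If the FAS is the denominator, the subject lowers the percentage. SAP 11.1 does not say which applies.

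**Working it through.** **Following one subject through the rules**

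1. The subject self-injects at Baseline and is assessed, so is in the FAS (SAP 3.4.3).
2. An ADE follows and the subject withdraws from DV0004. By definition this is a failure (Protocol 4.1.1; SAP 2.2.1.1 and 11.1).
3. All primary data come from the Week 4 page (SAP 11.1). The two items counted there do not ask about withdrawal, and no adverse event or disposition data are used.
4. With no Week 4 self-injection there are no observed data, and the outcome-variable rule in SAP 3.1 removes the subject from the denominator.
5. The documents do not say which pages are completed after withdrawal. If a Week 4 page exists because someone else injected, SAP 11.1 excludes that assessment, so the outcome is the same.

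**Inputs for the size**

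- The plan gives no precision figure for this endpoint, so there is none to reproduce.
- N = 100 FAS subjects per arm, from the planned 200/2 (SAP 2.3.6).
- Interval: 90% exact binomial (SAP 11.1).
- k = withdrawals for an ADE before Week 4, and f = failures recorded on the Week 4 page. Neither is in the documents; both are assumed.

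**Formulas**

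- Observed-data percentage: (N − k − f)/(N − k)
- Early ADE withdrawals counted as failures: (N − k − f)/N
- Gap: k(N − k − f)/[N(N − k)], which is k/N when f = 0
- Clopper-Pearson limits for x of n: the 5% quantile of Beta(x, n − x + 1) and the 95% quantile of Beta(x + 1, n − x). When x = n the lower limit is 0.05^(1/n), for example 0.05^(1/97) = 97.0%, and the upper limit is 100%.

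**Results**

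| k | f | Observed data (90% CI) | Counted as failures (90% CI) | Gap, points |
|---|---|---|---|---|
| 1 | 0 | 99/99 = 100% (97.0-100) | 99/100 = 99.0% (95.3-99.9) | 1.0 |
| 3 | 0 | 97/97 = 100% (97.0-100) | 97/100 = 97.0% (92.4-99.2) | 3.0 |
| 5 | 0 | 95/95 = 100% (96.9-100) | 95/100 = 95.0% (89.8-98.0) | 5.0 |
| 10 | 0 | 90/90 = 100% (96.7-100) | 90/100 = 90.0% (83.6-94.5) | 10.0 |
| 3 | 2 | 95/97 = 97.9% (93.7-99.6) | 95/100 = 95.0% (89.8-98.0) | 2.9 |
| 5 | 2 | 93/95 = 97.9% (93.5-99.6) | 93/100 = 93.0% (87.3-96.7) | 4.9 |

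With f = 0 the observed-data percentage stays at 100% whatever k is. With k = 0 the two percentages coincide.

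**The case against.** **The denominator may already be the FAS.** The default in SAP 3.1 and the reference to all subjects and the FAS in SAP 11.1 support this. If it is, early withdrawals already lower the percentage. The default yields where something else is noted, however, and the outcome-variable rule in the same section is the more specific text. The competing wording does not clearly override it. What stands is that the plan supports two readings with different primary results.

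**The endpoint belongs to a visit.** The primary outcome is ability at Week 4, and SAP 11.2 applies the same method to Baseline. An ADE recorded on the Baseline page is therefore a failure in the secondary outcome. That is true, but it leaves the Week 4 percentage as it is, and an ADE that arises after the Baseline page is completed may be missed there too.

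**Nothing is hidden.** The denominator is displayed (SAP 3.1), ADEs leading to discontinuation are tabulated (SAP 10.2.1), and discontinuations are summarised with reasons (SAP 5.1). A reader can see the loss. The primary estimate and its interval remain uncorrected.

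**Stronger readings that the documents do not support**

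- *That the primary percentage is biased in the device's favour overall.* This holds only for the denominator taken alone. The Week 4 item fails a subject for any device-related event, serious or not, which is stricter than the definition and pulls the other way. The net direction is unknown.
- *That the withdrawal criterion can almost never act.* An ADE entered on the Week 4 page does count, through that stricter item, and subjects may withdraw at any time up to the Week 5 call.
- *That a comparison of the two devices is distorted.* No comparison is planned.

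**Conclusion.** The point holds in this limited form. On the most specific reading of SAP 3.1 with SAP 11.1, a FAS subject who withdraws from DV0004 because of an ADE after the Baseline injection is in neither part of the Week 4 fraction, although the definition makes the event a failure. Through the denominator alone, the percentage is too high by about k points for k such subjects per 100. The size rests on an assumed k and on 100 FAS subjects per arm; such withdrawals may be rare or absent. There is no success threshold or hypothesis test, so no formal decision is affected. It still deserves correction before analysis, because the stated rules do not carry out the endpoint's own definition, and an equally literal reader could compute a different primary result.

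**What to change.** Add to SAP 11.1: *A FAS subject who has no Week 4 self-injection because of a SADE, or because of an ADE leading to withdrawal from DV0004, occurring after the first self-injection is counted as not having a safe and effective self-injection at Week 4 and remains in the denominator. This overrides the observed-data rule of Section 3.1. The reason is taken from the adverse event and disposition data.*

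State alongside it that subjects without Week 4 data for unrelated reasons are still handled as observed cases, and that subjects who do self-inject at Week 4 are assessed on that injection. The second statement matters: an earlier SADE should not by itself turn a clean Week 4 self-injection into a failure.

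The cost is this short addition and one merge with data already collected. No visit, procedure or clinical rule changes. The downside for the sponsor is that the reported percentage may be slightly less favourable.

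The mismatch between the any-device-related-event item and the narrower definition is a separate matter, which this text does not settle.
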